## A . OBJECT

Menstrual disorders are one of the most common clinical symptoms in women. Since puberty, about 70% of women have experienced menstrual disorders, including early, delayed, shortened, prolonged, and more importantly oligomenorrhea, amenorrhea, and decreased menstrual flow. At present, the main method of western medicine for the treatment of menstrual disorders is hormone replacement therapy, but the incidence of adverse reactions is high, and the clinical effect is mediocre. Traditional Chinese medicine in my country mostly adopts holistic conditioning therapy for the treatment of irregular menstruation.

Zhenqi Buxue Oral Liquid consists of sheep placenta, pearl, red ginseng, wolfberry, astragalus, angelica, coix seed, ginger and jujube. The excipients are protein sugar and sodium benzoate. Nourishes qi and blood. It is suitable for dizziness, pale complexion, fatigue, lack of energy and lazy words caused by insufficient qi and blood. This study will conduct a comprehensive and in-depth study on its treatment of mental and psychological stress and menstrual disorders with "oligomenorrhea, amenorrhea, amenorrhea and decreased menstrual flow" as the main manifestations. The molecular mechanism and clinical improvement, and the safety and adverse reactions of its use will be clarified.

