## B. STUDY METHOD AND DESIGN

- 330 women with menstrual disorders were observed in a prospective multi-center randomized controlled clinical trial.
- Inclusion Criteria:
  - 1) Aged between 25 and 40 years old;
  - 2) Patients with oligomenorrhea or oligomenorrhea or menopause within three months (see Appendix 1: Diagnostic Criteria of Traditional Chinese and Western Medicine)
  - 3) Meet the clinical medication conditions for progesterone to regulate menstruation
  - 4) The research subjects were informed and voluntarily participated in this study, and signed the informed consent at the same time.
- Exclusion Criteria:
  - 1) Age <25 years or >40 years old, pregnant or breastfeeding women
  - 2) Ovarian dysfunction caused by local ovarian surgery, radiotherapy and

chemotherapy for previous malignant tumors, taking hormones or immunosuppressive drugs;

- 3) Combined with serious or unstable physical diseases that may affect the efficacy of drugs and the conduct of trials, including liver, kidney, gastrointestinal, cardiovascular, respiratory, endocrine, neurological, immune or blood system diseases, etc., mental patients .
- 4) Those who were allergic to the drugs used in the trial or had serious adverse reactions in the past;
- 5) Breast cancer or family history of breast cancer in first-degree relatives, irregular vaginal bleeding, uterine fibroids ( $\geq 3$ cm), endometriosis, atypical endometrial hyperplasia, endometrial cancer and other hormone-dependent reproduction Systemic diseases and other malignant tumors;
- 6) Those with a history of thromboembolic disease or thrombosis;
- 7) Participated in a clinical trial of another research drug within 3 months prior to inclusion in this study (the first interview);
- 8) Those who have used related drugs in the past 3 months or have abused or depended on substances (alcohol or drugs) in the past 3 months; heavy smokers (smokers who smoke 20 or more cigarettes per day);
- 9) Those who met the inclusion criteria, did not follow the doctor's advice, were unable to judge the curative effect or were unable to evaluate the curative effect due to incomplete data.

➤ Methods: The participants were divided randomly into 3 groups:

- 1) Experimental group1(Zhenqi Buxue Oral Liquid): Zhenqi Buxue Oral Liquid, 10 ml each time, 2 times a day for 3 menstrual cycles, orally

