- 2) Experimental group2(Zhenqi Buxue Oral Liquid and Progesterone Capsules): Zhenqi Buxue Oral Liquid was taken orally, 10 ml at a time, twice a day for 3 menstrual cycles + orally from the second half of menstrual cycle, Progesterone Capsules 200mg, once a day for 10 days for 3 menstrual cycles
- 3) Active Comparator group (Progesterone Capsules): Progesterone Capsules 200mg, qd\*10 days\*3 menstrual cycles, orally

- Treatment Period: 3 month.
- Outcomes Measurement:
  - 1) Primary Outcome: Menstrual improvement in women including cycle period, menstrual volume, number of days with bleeding or spotting, monthly rates of amenorrhea
  - 2) Secondary Outcome:
    - a) Sex hormone levels: mainly FSH, LH, E2 and AMH
    - b) AFC: Changes in AFC in pelvic ultrasonography
    - c) SF-36: The change of the MOS item short from health survey
  - 3) Safety Assessment: Adverse reactions, Hepatic Function, Renal Function, Blood Glucose, Breast Ultrasound

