**Follow-up 3 (the third month after taking the medicine, equivalent to the end of the third month)**

- a) Ask and record adverse events that have occurred since enrollment;
- b) perform routine physical examinations (heart rate, blood pressure, weight);
- c) Ask the patient about the current menstruation and irregular menstruation symptoms, (or pregnancy), perform symptom scores, and evaluate the effectiveness of the drug;
- d) FSH, LH, E2, PRL, T, AMH (blood draw on day 2-3 of menstruation);
- e) Liver and kidney function;
- f) Pelvic ultrasound (bilateral ovarian AFC) examination, breast ultrasound;
- g) Subject returns untaken medication and checks (including used medication packaging) and filled diary card.

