**D. STATISTICS ANALYSIS**

Data was analyzed using SPSS Version 25. All quantitative information are expressed as mean values  $\pm$  standard deviation (SD). Statistical significance was assessed using unpaired Student's t-test or chi-square test. Probability values of less than 0.05 were considered significant and an asterisk identifies such significance in the figures. We will also compare the adverse effect of each group using descriptive statistics.

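### The secondary outcome list is open-ended, and every result falls under one unadjusted p<0.05 rule with no tier or contrast named, so a false significant secondary result is likely

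*Combined protocol and SAP*

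**What the plan says.** Section B (Outcomes Measurement) gives three secondary items: "Sex hormone levels: mainly FSH, LH, E2 and AMH", "AFC: Changes in AFC in pelvic ultrasonography" and "SF-36: The change of the MOS item short from health survey". Read literally, that is four named hormones, one ultrasound count and one questionnaire with no score chosen. No key secondary outcome, order or favourable direction is given.

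Section C draws two further hormones. Follow-up 3 lists "FSH, LH, E2, PRL, T, AMH (blood draw on day 2-3 of menstruation", and the screening visit draws the same six. SF-36 appears in none of the visits in Section C.

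On groups, Section B says: "The participants were divided randomly into 3 groups". On tests, Section D says: "Statistical significance was assessed using unpaired Student's t-test or chi-square test". On the threshold it says: "Probability values of less than 0.05 were considered significant and an asterisk identifies such significance in the figures". Section D has no global three-group test, named contrast, adjustment or exploratory label. Section A sets the aim: "The molecular mechanism and clinical improvement, and the safety and adverse reactions of its use will be clarified".

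**The concern.** The word *mainly* lets PRL or T join the secondary results after the data are seen. Two-sample tests in three groups with no contrast named leave one, two or three comparisons per outcome open. The significance rule treats a secondary result exactly like a primary one.

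As written, a hormone or AFC difference at p<0.05 is called significant even if every primary menstrual measure is null. The hormones and AFC are the only listed biological efficacy outcomes, so they are where a statement about mechanism would naturally look for support. With no favourable direction stated, a difference either way could be presented as an effect. Repairing the multiplicity of the primary outcome alone would not close this route.

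**Working it through.** **The plan's own figure.** The only error rate given is 0.05 per test (Section D). There is no family-wise figure to reproduce.

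**Inputs from the documents.** Three groups (Section B). Five secondary outcomes with a scheduled measurement: FSH, LH, E2, AMH, AFC (Sections B and C). A sixth, SF-36, is listed but not scheduled; it is counted below as one score.

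**Assumptions.** No true effect; two-sided tests; one time point; equal groups (330/3 = 110); a common between-outcome correlation ρ from 0 to 0.9. The documents give no correlation and no allocation ratio.

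**Step 1: one outcome.** The chance of at least one p<0.05 is:
- one contrast: 5%;
- two contrasts sharing the progesterone group: 9.07%, from the bivariate normal with correlation 0.5 between the two test statistics;
- all three pairs: 1 − F(1.96√2; 3 groups, df = ∞) = 12.23%, where F is the studentized-range distribution function.

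**Step 2: independent outcomes (ρ = 0).**
- Five outcomes: 1 − 0.95^5 = 23%; 1 − 0.9093^5 = 38%; 1 − 0.8777^5 = 48%.
- Six outcomes: 1 − 0.95^6 = 26%; 1 − 0.9093^6 = 43%; 1 − 0.8777^6 = 54%.

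Treating the 6 × 3 = 18 tests as independent would give 1 − 0.95^18 = 60%. That is too high, because the pairs share groups.

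**Step 3: correlated outcomes.** The standardised mean of group g on outcome k was simulated as √ρ·U_g + √(1−ρ)·E_gk, with U and E independent standard normal. A pair is declared different when its absolute difference divided by √2 exceeds 1.96. Chance of at least one false significant result:

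| Outcomes | Contrasts | ρ = 0.9 | ρ = 0.5 | ρ = 0 |
|---|---|---|---|---|
| 5 scheduled | one | 10% | 18% | 23% |
| 5 scheduled | two vs progesterone | 18% | 31% | 38% |
| 5 scheduled | all three pairs | 23% | 39% | 48% |
| 6 (with SF-36) | one | 11% | 21% | 26% |
| 6 (with SF-36) | two vs progesterone | 19% | 35% | 43% |
| 6 (with SF-36) | all three pairs | 24% | 44% | 54% |

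Actual t-tests at 110 per group gave 54.2% for six independent outcomes and all pairs, so the normal approximation is adequate.

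**Step 4: effect of the open list.** Adding PRL and T to the five scheduled outcomes makes seven. For all pairs at ρ = 0 this is 1 − 0.8777^7 = 60%.

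**Step 5: check of a Holm remedy.** Under the global null, Holm's family-wise error equals that of its first step.
- Run separately within each contrast on five outcomes (first step 0.05/5) at ρ = 0: 4.9% for one contrast, but about 9% over two and 13% over three.
- Run once over all 5 × 3 = 15 tests (first step 0.05/15): 4.6%, 4.0% and 2.3% at ρ = 0, 0.5 and 0.9.

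**The case against.** Outcomes labelled secondary are often tested without adjustment, and Section B does keep the two tiers apart. No sentence says that a secondary p<0.05 will support an efficacy or mechanism conclusion, and the aim in Section A is not tied to these outcomes. All of this stands. It rules out saying that the sponsor plans false claims, but it does not supply the exploratory label that Section D lacks.

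A reader might infer that the plan tests every pair. It does not say so. Because one arm is labelled the active comparator, the two contrasts with progesterone are at least as natural a reading, which is why all three cases are shown.

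A reader might also infer that every secondary result will carry an asterisk. Section D mentions asterisks only for figures and does not say which outcomes will be plotted. The rule that p<0.05 is significant has no such limit.

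Counting eight SF-36 scales would push the rate far higher, but no visit collects the instrument, so the documents do not support that count.

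Finally, the missing contrast and adjustment in Section D also affect the primary outcome, where they matter more. One rule there could serve both tiers. The open list, the unscheduled SF-36 and the status of the secondaries would still need their own wording.

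**Conclusion.** The point holds in a conditional form. With five scheduled outcomes and ρ from 0.9 to 0, the chance of at least one false significant secondary result is about 10-23% for one contrast, 18-38% for two and 23-48% for three. With SF-36 as one score it is 11-26%, 19-43% and 24-54%.

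These rates assume no true effect on any outcome, and they count differences in either direction, not only those favouring the oral liquid. The upper figures are not a ceiling, because the list is open.

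A reader might conclude that the trial breaches a stated 5% error rate. It does not: 5% is a per-test threshold and the documents state no family-wise rate. The defect is that nothing limits what may be concluded from the secondary results. It should be corrected, but it is not an error in the primary analysis.

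**What to change.** **Section B.** Delete *mainly* and close the list to FSH, LH, E2, AMH, AFC and SF-36, naming the SF-36 score in advance. Reconcile SF-36 with the visits in Section C, or leave it out of the tested list. Report PRL and T descriptively.

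**Section D.** State that secondary outcomes are exploratory: estimates with 95% intervals, no significance asterisk, and no efficacy or mechanism conclusion drawn from them alone.

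**If confirmatory secondary claims are wanted.** First define one primary test, which the plan does not yet do. Test secondaries only after it succeeds. Apply Holm at 5% across all secondary outcomes and all contrasts carried forward together, not separately within each contrast. State each outcome's favourable direction beforehand.

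**Cost.** Wording in Sections B and D, fixed before the data are analysed, with no extra patients, visits or assays. Keeping SF-36 also means adding the questionnaire to the schedule in Section C. The downside is that some unadjusted p<0.05 differences in hormones, AFC or SF-36 could no longer be presented as significant.

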**Follow-up 1 ( equivalent to the end of the first month)**

- a) Ask and record adverse events that have occurred since enrollment;
- b) Ask the patient about the first menstrual condition (menstrual period, cycle, menstrual volume) and symptoms of irregular menstruation after taking the medicine and make a score;
- c) The investigator and the subject agree on the time of the next follow-up visit.

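### Visits record adverse events, but the clinical-event safety outcome is an undefined 'adverse reactions', so the between-arm comparison may rest on unblinded attribution

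*Combined protocol and SAP*

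**What the plan says.** The protocol uses three different words for harm at three stages.

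- **Collection** (Section C, Follow-up 1, with the same instruction at Follow-ups 2 and 3): "Ask and record adverse events that have occurred since enrollment".
- **Outcome** (Section B, Outcomes Measurement): "Safety Assessment: Adverse reactions, Hepatic Function, Renal Function, Blood Glucose, Breast Ultrasound".
- **Analysis** (Section D): "We will also compare the adverse effect of each group using descriptive statistics".

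Safety is a stated aim: Section A says that "the safety and adverse reactions of its use will be clarified". Section A also says of hormone replacement therapy in general that "the incidence of adverse reactions is high, and the clinical effect is mediocre".

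The document defines none of the three terms. It gives no causality categories, assessor or counting unit for clinical events. It does not say whether the trial is open-label or blinded. It mentions no placebo, dummy or blinded assessor.

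**The concern.** An adverse event is usually anything untoward that happens to the patient, and an adverse reaction is the subset judged to be caused by the drug. Read that way, the plan collects the full set and reports a subset, and the step between them is left to judgement without a rule.

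That matters here because the arms are easy to tell apart: a twice-daily liquid, the liquid plus capsules, or capsules alone for ten days per cycle. Whoever decides whether a complaint is drug-related will probably know the treatment, and the rationale already expects hormone therapy to cause many reactions. If events are attributed more readily in one arm than another, the reported rates will differ even when the true rates do not.

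The undefined terms also leave open, until after the data are seen, which count will be reported.

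**Working it through.** The plan gives no safety rate to reproduce, so the check has two parts.

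**1. Does anything link the three terms?**

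| Stage | Term used | Definition | Rule leading to the next stage |
|---|---|---|---|
| Visits (Section C) | adverse events | none | none |
| Outcome (Section B) | adverse reactions | none | none |
| Analysis (Section D) | adverse effect | none | not applicable |

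Nothing does. Two readings are therefore open. If the terms are synonyms, all recorded events are compared and no attribution step exists. If adverse reactions carries its usual meaning, an unwritten attribution step decides the count. The other items on the outcome line are laboratory or imaging measures and need no attribution under either reading.

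**2. How large could the distortion be under the second reading?**

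Inputs:
- Total of 330 women in three randomised groups (Section B). The allocation ratio is not stated. Equal allocation is assumed: 330 / 3 = 110 per arm.
- True risk of an adverse event: assumed equal in the liquid and progesterone arms.
- Share of events judged drug-related: assumed. The documents give no figure.
- Simplification: one event per affected woman.

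Formula: reported rate = true risk × share attributed to drug.

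| True risk, both arms | Attributed: liquid / progesterone | Reported: liquid v progesterone | Spurious difference (percentage points) |
|---|---|---|---|
| 20% | 60% / 60% | 12% v 12% | 0 |
| 20% | 50% / 70% | 10% v 14% | 4 |
| 20% | 40% / 60% | 8% v 12% | 4 |
| 20% | 30% / 60% | 6% v 12% | 6 |
| 20% | 40% / 80% | 8% v 16% | 8 |
| 10% | 50% / 70% | 5% v 7% | 2 |
| 10% | 40% / 80% | 4% v 8% | 4 |
| 30% | 30% / 60% | 9% v 18% | 9 |
| 30% | 40% / 80% | 12% v 24% | 12 |

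Example: 0.20 × 0.30 = 0.06 and 0.20 × 0.60 = 0.12. At 110 per arm that is about 110 × 0.06 = 6.6 women against 110 × 0.12 = 13.2 women.

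The difference is 0 whenever the attribution shares are equal. If every recorded event is counted, both shares are 100% and the expected difference is 0 in every row (20% v 20% in the example).

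**Precision at 110 per arm**, using 1.96 × √[p₁(1−p₁)/110 + p₂(1−p₂)/110]:
- Reported 6% v 12%: 1.96 × √(0.0564/110 + 0.1056/110) = 1.96 × 0.0384 = 0.075. The difference is 6 points, 95% CI about −1.5 to 13.5.
- All-cause 20% v 20%: 1.96 × √(2 × 0.16/110) = 1.96 × 0.0539 = 0.106. The difference is 0, 95% CI about ±10.6 points.

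A doubling of the reported rate can therefore look striking in a descriptive table although its interval includes zero. For that reason the table should carry intervals.

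**The case against.** The strongest reply is that no causality step is written anywhere. The visits simply record events, and the English is loose elsewhere (the inclusion criteria list the same condition twice), so the three terms may be synonyms. All recorded events would then be compared and the bias could not arise. This stands as a possibility, and it is why the point is conditional. It does not remove the need to settle the wording, because the reader cannot tell which count will be reported.

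Several stronger readings are tempting, and the documents do not support them:

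- **That safety counts only drug-attributed events.** The same outcome line lists hepatic and renal function, blood glucose and breast ultrasound.
- **That assessors are known to be unblinded.** Masking is not stated either way. Open-label conduct is likely from the visibly different regimens and the absence of any dummy, but it remains an inference.
- **That the trial is set up to announce fewer reactions on the liquid.** No such hypothesis is stated. The primary outcome is menstrual improvement, and the remark in Section A concerns hormone replacement therapy generally, not these capsules.
- **That a significance test would falsely call the liquid safer.** A chi-square test on 6% v 12% would do so in about 35% of trials under the assumed figures. Section D assigns descriptive statistics to adverse effects, not a test, so that figure does not describe the plan.
- **That one early event would be counted three times**, because each visit asks back to enrolment. At Follow-up 1 that is the same interval as since the last contact. No event-based count is planned, and asking cumulatively is not counting cumulatively.

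**Conclusion.** The point holds in a limited, conditional form. The mismatch between what is collected, what is listed as the outcome and what is analysed is plain in the text. If adverse reactions means drug-related events, the clinical-event comparison between arms rests on attribution with no stated rule, probably by people who know the treatment.

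For the attribution patterns tried, the spurious difference is 2 to 12 percentage points, and 6 points (6% v 12%) in the central example. These sizes rest on assumed true risks, assumed attribution shares and an assumed 110 women per arm. They show what unequal attribution would do and are not evidence that it will occur. The laboratory and ultrasound safety measures are outside the point.

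Severity is minor to moderate. Safety is a stated aim and the remedy is nearly free, but the planned analysis is descriptive, so the harm would be a misleading table and not a false test result.

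**What to change.** - **Section B, Safety Assessment:** replace *Adverse reactions* with *all adverse events regardless of judged cause*, and use that one term throughout.
- **Section D:** make the main clinical safety summary the number and percentage of women with at least one adverse event of any cause, by arm, with between-arm differences and 95% CIs. Show drug-related events only in a secondary table, under a causality rule written down in advance that says who judges and on what categories.
- **Section C:** no change is needed for this point. Counting women, not events, makes the repeated questions back to enrolment harmless.

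The cost is wording only, because the events are already recorded at every visit. No visit, test or participant is added, and the sample size is unaffected.

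There are two downsides. All-cause rates will look higher in every arm and will include unrelated illness. Removing the attribution step also does not remove all bias: if the trial is unblinded, what women report and how staff ask could still differ by arm, and the report should say so.

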## **C. TECHNICAL ROUTE**

### **Screening Period (Day -30~0)**

- a) The researcher explained the research situation and informed the subjects, and the subjects signed the informed consent;
- b) Evaluate whether subjects can enter the study according to the inclusion and exclusion criteria;
- c) Collect basic information, medical history (including menstrual history, pregnancy and birth history) and demographic data, conduct routine physical examination (heart rate, blood pressure, height, weight); and irregular menstrual symptoms and scoring
- d) On the 2nd to 3rd day of the menstrual cycle (basic day), draw venous blood to check FSH, LH, E2, prolactin (PRL), testosterone (T), and AMH;
- e) Liver and kidney function;
- f) Pelvic ultrasound: on the 1st to 3rd day after menstruation is clean, after disinfection of the vulva, transvaginal ultrasound is performed to count bilateral ovarian AFC, breast ultrasound;
- g) The investigator and the subject agree on the time of the next follow-up visit.

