**Follow-up 2 (After taking the medicine in the second month, follow-up by WeChat or telephone)**

- a) Ask and record adverse events that have occurred since enrollment;
- b) Ask the patient about the second menstrual condition (menstrual period, cycle, menstrual volume) and the symptoms of irregular menstruation after taking the medicine and make a score;
- c) The investigator and the subject agree on the time of the next follow-up visit.

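### The baseline for menstrual improvement is not specified at screening, and the planned analysis makes no use of one

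*Combined protocol and SAP*

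**What the plan says.** Section B of the combined protocol and SAP gives the primary outcome as "Menstrual improvement in women including cycle period, menstrual volume, number of days with bleeding or spotting, monthly rates of amenorrhea". It does not define improvement or name a reference period.

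Section C, Screening Period, item c, is where the pre-treatment menstrual information is collected: "Collect basic information, medical history (including menstrual history, pregnancy and birth history) and demographic data". After a routine physical examination, the same item ends "and irregular menstrual symptoms and scoring". The contents of the menstrual history are not listed, no look-back is set, and the score is not described.

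Follow-up 1 is more specific: "Ask the patient about the first menstrual condition (menstrual period, cycle, menstrual volume"), plus the symptom score. Follow-up 2 asks for the same three items and the score for the next menstruation. Follow-up 3 asks about the current menstruation and symptoms, with a score, without naming cycle, duration or volume. It also collects a diary card whose contents and start date are not given.

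Section D offers an unpaired t-test or a chi-square test. It mentions neither a change from baseline nor a baseline covariate.

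**The concern.** Improvement is a comparison with an earlier state, so each primary component needs a recorded earlier value. The plan does not ensure that one exists in usable form. The trial is multi-center, and an unitemised history lets each center record different things over different periods. Screening covers only the 30 days before enrolment. In women recruited for infrequent or absent periods, that window may hold one bleed or none, so cycle length and monthly amenorrhoea need an explicit look-back.

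The secondary outcomes are better anchored: the hormones and the antral follicle count have specified screening measurements.

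Two things are at stake. Without a stated reference, improvement may be judged in retrospect at Follow-up 3, where the effectiveness of the drug is evaluated. The text describes no placebo or blinding, so the women may know their treatment by then. Second, women differ in how infrequent or light their periods are at entry. An analysis that ignores baseline leaves that spread in the error term.

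**Working it through.** **Visits side by side**

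| Item | Screening | Follow-ups 1 and 2 | Follow-up 3 |
|---|---|---|---|
| Cycle length | only if the history captures it | itemised | not itemised |
| Menstrual volume | only if the history captures it | itemised | not itemised |
| Days of bleeding or spotting | only if the history captures it | period itemised, spotting not named | not itemised |
| Months without a bleed | only if the history captures it | not itemised | not itemised |
| Symptom score | yes, undefined | yes, undefined | yes, undefined |
| Hormones, antral follicle count | yes | no | yes |

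The symptom score has a matching baseline but is not one of the four primary components. None of those four has an assured baseline. Spotting days and amenorrhoea are itemised at no visit, so for these the follow-up value is under-specified too.

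**Size of the precision loss (illustration, continuous components only)**

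The plan gives no power calculation, so there is no figure to reproduce. Inputs:
- Total size 330: "330 women with menstrual disorders were observed in a prospective multi-center randomized controlled clinical trial" (Section B).
- Baseline to follow-up correlation r: not in the documents; assumed 0.3 to 0.6.

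Under linear covariate adjustment, the share of error variance removed is r², and the equivalent sample size is 330/(1 − r²).
- r = 0.3: r² = 0.09, so 9% is removed; 330/0.91 = 363.
- r = 0.6: r² = 0.36, so 36% is removed; 330/0.64 = 516.

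**The same effect as power for one pairwise comparison**

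Further assumptions: 110 per arm (equal split into three; the ratio is not stated), two-sided alpha 0.05 (sidedness is not stated), and a standardised difference d = 0.378, chosen to give 80% power without adjustment. Power = Φ(d/(s·√(2/110)) − 1.96), where s is the SD multiplier and √(2/110) = 0.135.
- Follow-up value only, s = 1: power 80%.
- Baseline-adjusted (ANCOVA), s = √(1 − r²): 84% at r = 0.3 and 90% at r = 0.5.
- Simple change score, s = √(2(1 − r)): 66% at r = 0.3 and 80% at r = 0.5.

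The last line shows why the baseline should enter as a covariate rather than only by subtraction: with a modest correlation, a change score is less precise than ignoring baseline.

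**The case against.** The strongest case against is that missing detail is not missing data. A menstrual history would plausibly cover cycle, duration and volume. Inclusion criterion 2 carries a three-month reference and is checked at screening and again on Day 1, so some pre-treatment cycle information must be obtained. Appendix 1, which holds the diagnostic criteria, is cited but is not in the text supplied and cannot be judged. This stands: the fault is lack of specification, not proven absence.

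A reader might infer three stronger things that the documents do not support:
- *That there is no menstrual baseline at all.* The symptom score is taken at screening and at all three follow-ups.
- *That chance imbalance in severity can be neither seen nor corrected.* The score, the history, the hormones and the antral follicle count are all collected before randomisation. They would show some imbalance, though not necessarily in the primary components themselves.
- *That the group comparison is invalid.* Allocation is random ("The participants were divided randomly into 3 groups"), so on-treatment values can be compared fairly without any baseline.

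The size is also open to challenge. The r² formula does not carry over to monthly amenorrhoea, and it compares adjustment with using no baseline information, so the gain beyond the existing score and history would be smaller. New form fields gain no precision unless Section D changes as well. Finally, if follow-up values come from the diary card while baseline comes from recall, r may fall below the assumed range. These limits are accepted. They reduce the size of the gain, not the case for specifying the baseline.

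**Conclusion.** The concern holds in a limited form. The plan does not specify that the four primary components are recorded before randomisation over a defined period and in the form used later, so the reference for improvement is undefined. The planned tests would not use a baseline even if it were recorded. This weakens the meaning of the primary outcome and its precision; it does not bias the randomised comparison.

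The range of 363 to 516 equivalent women rests entirely on an assumed correlation of 0.3 to 0.6, applies to cycle length, bleeding days and volume only, and shrinks if recall is poor. The definitional gap does not depend on any of these assumptions. This is a cheap improvement that should be made, not a fatal flaw.

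**What to change.** 1. **Section C, Screening, item c.** Before randomisation, record for the previous three months: cycle length (from the onset date of each bleed), days of bleeding or spotting, menstrual volume, and months without a bleed. Three months matches the length of treatment.
2. **Section C, Follow-ups 1, 2 and 3.** Record the same four items on the same form at each visit. Itemising the baseline alone would leave spotting days and amenorrhoea without a specified follow-up value, and Follow-up 3 with none of the four.
3. **Section B, primary outcome.** Define improvement for each component against its baseline value.
4. **Section D.** Replace the unpaired tests for these outcomes with baseline-adjusted comparisons: ANCOVA with the baseline value as covariate for cycle length, bleeding days and volume, and logistic or similar regression with baseline amenorrhoea as covariate for the monthly amenorrhoea rate.

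The cost is a few case report form fields at existing visits and a short rewrite of the outcome definition and Section D. The main downside is recall error at baseline. Because the value is recorded before randomisation, that error does not differ systematically by arm; it lowers the correlation, and with it the precision gained. The record must be made before dosing starts, since recall after that point could be coloured by experience of the treatment.
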